4.5.4. Vital Signs and Physical Examination

The actual value and change from baseline (Day 1, or in general, the last evaluation prior to initiation of study treatment) to each on-study evaluation will be summarized for vital signs for all study patients combined.

[figure not shown]
Vital sign measurements will be presented for each patient in a data listing.

Physical examination results at screening will be summarized.

All physical examination findings will be presented in data listings.

Relevant Output

CCI

[figure not shown]
4.5.5. Electrocardiogram

ECG results will be summarized descriptively, including heart rate and PR, QRS, QT, and QTc (calculated by the Fridericia correction formula) intervals. QTc intervals calculated by the Bazett formula will be transformed to Fridericia. The Fridericia corrected QTc interval (QTcF) will be derived using the formula:  $QT/(RR^{(1/3)})$ , where  $RR = 60/\text{heart rate}$ . Actual values and changes from baseline will be reported for each study visit.

ECG data for each patient will be provided in a data listing.

Relevant Output

CCI

[figure not shown]
4.5.6. Neurological Examinations

Neurological examination findings will be presented via shift tables, summarizing the changes from baseline to worst value for each parameter.

All neurological examination findings will be presented in a data listing.

Relevant Output

CCI

CCI

[figure not shown]
#### 4.5.7. Ophthalmic Examinations

Ophthalmic examination results for visual acuity, tonometry, slit lamp exam, and dilated funduscopy at each time point will be summarized.

All ophthalmic examination findings will be presented in data listings.

#### Relevant Output

CCI

#### 4.5.8. Concomitant Medications

Concomitant medication is defined as any prescription or over-the-counter preparation, including vitamins and supplements. Patients may continue their baseline medication(s), but all concomitant medication(s) must be reported in the eCRF. Any diagnostic, therapeutic or surgical procedure performed during the study period should be recorded, including the dates, description of the procedure(s) and any clinical findings.

Patients will receive concomitant medications to manage cancer symptoms, AEs, and intercurrent illnesses that are medically necessary as standard care. Medications to treat concomitant diseases like diabetes, hypertension, etc. are allowed.

Concomitant medications will be coded using the WHO Drug Dictionary. Results will be tabulated by anatomic therapeutic classification (ATC) and preferred term.

Concomitant medications will be tabulated by cohort and overall, where any medications that did not end prior to first dose of study medication and any medications started after the first dose of study medication will be included. If an end date is missing or the medication is ongoing, the medication will be included in the tabulation.

The use of concomitant medications and concomitant procedures will be included in a by-patient data listing. Separate by-patient listings will present prophylactic therapies and antineoplastic therapies received following study drug.

[figure not shown]
Relevant Output

CCI

## 5. CHANGES TO PLANNED ANALYSES

CCI

In Protocol Section 8.4.1, it is noted that no imputation of missing efficacy data is planned. In Section 3.10 of this document, it is noted that partial time-to-event dates with only month and year available will be imputed by setting the day to the first day of the month.

Protocol Section 8.3 describes 3 populations (mITT, PP, and Safety population) to be used for study analyses. In Section 2.1 of this document, two additional populations are included, the GCIG Evaluable population and the mITT Extended population. In addition, the mITT population definition is updated to include the criterion that patients have measurable disease per RECIST v1.1 at baseline.

[figure not shown]

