1.3 Study Rationale

Selinexor has demonstrated potent anti-cancer activity in models (in vitro and in vivo) hematologic and solid cancers including ovarian, endometrial and cervical cancers (see *Selinexor/KPT-330 IB*).

In an ongoing Phase 1 dose escalation study in patients with advanced solid tumors (KCP-330-002), a selinexor dose of 50 mg/m² twice weekly was tolerated and cleared DLT evaluation. Based on the Phase 1 results, the original doses and schedules for selinexor were chosen for the current study. During the conduct of the study, as a result of new findings regarding selinexor tolerability, and regulatory authority interactions regarding the overall selinexor development program, the recommended doses and schedules in Part 2 were revised to 35 mg/m² twice weekly or 50 mg/m² once weekly (depending on the patient population).

In KCP-330-002, selinexor has induced > 16-week disease control in several patients with R/R gynaecologic tumors. Patients with cervical adeno- and squamous carcinomas had stable disease for ≥ 6 cycles (24 weeks). Of six ovarian cancer patients treated to date, one has a 28% tumor reduction, another has stable disease with slight reduction in CA-125 levels, and a third has stable disease on first computed tomography (CT) scan. This data further supports the development of KPT-330 for the therapy of gynaecological cancers.

Ovarian, endometrial, and cervical cancers are sensitive to anti-neoplastic chemotherapy. Despite this fact, the majority of women with advanced ovarian, cervical and endometrial cancer will ultimately relapse. Altogether, in all three types of gynaecologic malignancies, the treatment of patients with advanced or relapsed disease remains difficult. Thus, new therapy options for women with these diseases are urgently needed.

In the current ongoing study, selinexor has shown promising results. An interim analysis of 12-week DCR data at the end of Stage 1 IA in evaluable patients (as of 29 April 2015) reported:

- 6 out of 8 patients for Cohort A (75%) (95% CI, 34.9 – 96.8)
- 5 out of 8 patients for Cohort B (62.5%) (95% CI, 24.5 – 91.5)
- 2 out of 8 patients for Cohort C (25%) (95% CI, 3.2 – 65.1)

1.4 Rationale for the Maintenance Phase (Continued Access to Treatment following termination of Primary Treatment Phase)

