 11. The patient must be recovered from any prior treatment/major operation. The treatment/major operation must be performed at least 4 weeks prior to start of study drug. Palliative radiotherapy is permitted until one week prior to the start of study drug.
 12. Only incurable patients with histologically or cytologically proven primary tumor and objective documentation of disease progression on prior treatment by CT/MRI may be enrolled.
 13. *Ovarian, fallopian tube, or peritoneal carcinoma*: both platinum refractory* and platinum resistant** patients, who have received ≥ 1 line of chemotherapy for relapsed disease (i.e., ≥ 2 lines of chemotherapy in total).
 - * Platinum refractory is defined as progression during or within 4 weeks of last treatment with a platinum-containing therapy.
 - ** Platinum resistant is defined as relapse 4 weeks to < 6 months after a platinum-containing therapy.
 14. *Endometrial carcinoma*: patients must have received ≥ 1 line of chemotherapy for relapsed or advanced (stage IV, IIIc) disease.
 15. *Cervical carcinoma*: patients must have received ≥ 1 line of chemotherapy for relapsed or advanced (stage IVb) disease.
 16. Carcinosarcomas (Malignant Mixed Mullerian Tumor) are allowed, but all other non-epithelial cancers of the ovary, fallopian tube, endometrium, or cervix are excluded.
 17. Patients must have either measurable disease per RECIST 1.1 or evaluable disease outside irradiated field on CT/MRI. For *ovarian cancer*: Patients must have disease that is measurable according to RECIST or assessable according to the GCIG CA-125 criterion. A rise in CA-125 or other tumor marker alone is not sufficient.

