8 STATISTICAL METHODS

8.1 Trial Design and Hypotheses

This trial has been designed as a multi-center, open-label, two-stage phase II study in 3 separate gynaecological cancer cohorts, with an additional set of patients in the ovarian cohort randomized into two different treatment regimens.

Study data may be analyzed and reported to competent regulatory authorities when $\geq 75\%$ of patients have completed at least ≥ 2 cycles of treatment or discontinued from the study.

The primary objective is to determine the efficacy of selinexor in patients with advanced or metastatic gynaecological cancers as assessed by disease control rate (DCR). Disease control rate (DCR) is defined as complete response (CR) or partial response (PR) or stable disease (SD) for at least 12 weeks, assessed according to RECIST 1.1. The Simon's⁹⁷ two-stage optimal design will be used to address the primary trial objective, with the following hypothesis to be tested for DCR for each cohort:

H_0 : true disease control rate ≤ 0.25 versus H_1 : true disease control rate ≥ 0.50 .

Secondary objectives are:

[figure not shown]
- Determine the efficacy of selinexor in patients with advanced or metastatic gynaecological cancers using:
 - Objective response rate (ORR)
 - Progression-free survival (PFS)
 - Overall Survival (OS) including OS rates at 12 and 24 months
- Evaluate safety and tolerability of selinexor in patients with advanced or metastatic gynaecological cancers.
- Evaluate QoL for patients with advanced or metastatic gynaecological cancers treated with selinexor.

Patients enrolled into the second part of the study in the ovarian cohort will be randomized using a centralized randomization via IWRS. Randomization will be performed within the ovarian cohort and will not be specific to the study site.

Complete details of data analysis and presentation will be included in a statistical analysis plan (SAP) which will be finalized prior to database lock.

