## **2. PATIENT POPULATIONS**

### **2.1. Population Definitions**

The following patient populations will be evaluated and used for presentation and analysis of the data:

- **Modified Intent-to-Treat (mITT) Population:** All patients who receive at least one dose of study medication, have measurable disease per RECIST at baseline, and have at least one post-baseline efficacy follow-up information. If the patient has measurable disease per RECIST at baseline, but discontinued treatment prior to the first assessment due to death, toxicity, or PD, they will still be included even if there is no post-baseline efficacy follow-up information. This population will be used for primary analyses of efficacy.
- **Per-Protocol (PP) Population:** All patients in the mITT population who are compliant with study assessments and who have no protocol violations that would compromise the assessment of efficacy. This population will be used for supportive inferences concerning efficacy. If there are major differences between the results in this population and those obtained in the mITT population, this will be taken into consideration in the decision to continue to later phase studies, or in the design of further studies.
- **GCIG Evaluable Population:** All patients in the ovarian cancer cohort (Cohort A) who receive at least one dose of study medication, have measurable disease per RECIST at baseline or a baseline CA-125 assessment, and have at least one post-baseline efficacy follow-up information (i.e. either a post-baseline scan or CA-125 assessment). If a patient discontinued treatment prior to the first assessment due to death, toxicity, or PD, they will still be included even if there is no post-baseline efficacy follow-up information. This population will be used for additional efficacy analyses specific to patients with ovarian cancer.
- **mITT Extended Population:** All patients who receive at least one dose of study medication and have at least one post-baseline efficacy follow-up information. If the patient discontinued treatment prior to the first assessment due to death, toxicity, or PD, they will still be included even if there is no post-baseline efficacy follow-up information. This population will be used for supportive efficacy analyses of select time-to-event endpoints (PFS and OS).

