#### 3.2. General Methods

All data listings that contain an evaluation date will contain a relative study day (Rel Day). Pre-treatment and on-treatment study days are numbered relative to the day of the first dose of study medication which is designated as Day 1. The preceding day is Day -1, the day before that is Day -2, etc. The last day of study medication is designated with an "L" (e.g., Day 14L). Post-treatment study days are numbered relative to the last dose and are designated as Day 1P, Day 2P, etc.

All output will be incorporated into Microsoft Word files, sorted and labeled according to the International Conference on Harmonization (ICH) recommendations, and formatted to the appropriate page size(s).

Tabulations will be produced for appropriate disposition, demographic, baseline, efficacy, and safety parameters. For categorical variables, summary tabulations of the number and percentage of patients within each category (with a category for missing data) of the parameter will be presented. For continuous variables, the number of patients, mean, median, standard deviation (Std Dev), minimum, and maximum values will be presented. Time-to-event data will be summarized using Kaplan-Meier (KM) methodology using 25th, 50th (median), and 75th percentiles with associated 2-sided 95% confidence interval (CI), as well as number and percentage of censored observations and events.

Data will be presented by study part, cohort, and schedule (Part 2 only) as follows:

- Part 1: Cohort A
- Part 1: Cohort B
- Part 1: Cohort C
- Part 2: Cohort A: Schedule 1
- Part 2: Cohort A: Schedule 2

Formal statistical hypothesis testing will be performed on the primary endpoint with all tests conducted at the one-sided 0.10 level of significance for Part 1 and at the two-sided 0.20 level of significance for Part 2. Summary statistics will be presented, as well as CIs on selected parameters, as described in the sections below.

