## **8.2. Statistical Analysis Plan Version 3.0: 07 April 2016**

### Rationale of Revisions

Changes were made to the SAP according to Protocol Version 3.1 dated 08 January 2016. Note that Protocol Version 4.0 was never submitted to an IRB or regulatory authority, so while the previous SAP and Randomization Plan were finalized off of that version, it is removed from the title page of this document. The randomization methodology has not been changed.

Changes throughout the document include minor editorial changes and the removal of Part 3, the breast cancer cohorts.

### Description of Revisions Affecting Section 1

CCI

- Section 1.2.1 Synopsis of Study Design was updated to include minor editorial changes and additional information regarding dose reductions and escalations.
- Section 1.2.3 Stopping Rules was updated to add further detail on reasons a patient may come off treatment.
- Section 1.2.4 Study Procedures was updated to include modifications to the schedule of assessments.
- Section 1.2.5.1 Efficacy Parameters was updated to include editorial changes, further clarification on endpoints, and the GCIG response criteria assessments for the ovarian cancer cohort.

### Description of Revisions Affecting Section 3

- Section 2.1 Population Definitions was updated to further define each efficacy population, including by adding 2 new populations (GCIG Evaluable and mITT Extended).
- Section 2.2 Protocol Violations was updated to include that violations will be assessed independent of knowledge of response to therapy.

### Description of Revisions Affecting Section 3

- Section 3.1 Sample Size Justification was updated to remove the planned breast cancer cohorts description.
- Section 3.2 General Methods was updated to clarify presentation of data.
- Section 3.8 Subpopulations was updated to include the subsets of ovarian patients with a baseline CA-125 assessment and with a baseline CA-125 assessment at least twice the upper limit of normal.
- Section 3.10 Missing, Unused, and Spurious Data was updated to include further detail on partial dates, both for time to event and baseline data. Detail on missing data for QoL analysis was also added.

### Description of Revisions Affecting Section 4

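### The SAP limits the primary mITT to measurable disease, and no RECIST 1.1 DCR analysis in the visible plan includes the eligible patients this removes

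*SAP*

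**What the plan says.** **Eligibility.** Protocol 4.2.1, item 17: "Patients must have either measurable disease per RECIST 1.1 or evaluable disease outside irradiated field on CT/MRI". For ovarian cancer, disease assessable by the GCIG CA-125 criterion is an alternative to RECIST-measurable disease. Protocol 5.1.1 repeats that evaluable-only patients may enter.

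**Primary population.** Protocol 8.3.1 defines the mITT by one dose plus a post-baseline efficacy assessment, with an exception for patients who stop early because of death, toxicity or progression. Measurable disease is not mentioned. SAP 2.1 adds it, and SAP 5 declares the change: "the mITT population definition is updated to include the criterion that patients have measurable disease per RECIST v1.1 at baseline".

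**Other populations in SAP 2.1.**
- Per-protocol is a subset of the mITT.
- mITT Extended is the mITT without the measurable-disease criterion, so in substance it is the protocol's mITT. Of it the SAP says: "This population will be used for supportive efficacy analyses of select time-to-event endpoints (PFS and OS".
- GCIG Evaluable (Cohort A only) takes patients with measurable disease or a baseline CA-125.

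**Analyses.** SAP 4.3 runs efficacy on the mITT and per-protocol sets. SAP 4.3.1 defines the primary RECIST 1.1 DCR, with control to at least 77 days and a lower one-sided 90% bound. SAP 4.3.2 uses mITT Extended for PFS and OS, and plans a GCIG-criteria DCR for Cohort A in both parts.

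**Dates.** Protocol 1.3 reports "An interim analysis of 12-week DCR data at the end of Stage 1 IA in evaluable patients" as of 29 April 2015. SAP 8.2, for Version 3.0 of 07 April 2016, says: "Section 2.1 Population Definitions was updated to further define each efficacy population".

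**The concern.** Patients whom the protocol deliberately made eligible are treated and scanned on the same schedule as the rest, then left out of the primary endpoint. When a primary population is narrowed in an open-label study in which early DCR results have already been reported, a reader needs to see the result on the population set out in the protocol. The SAP builds exactly that population but applies it only to two secondary endpoints. The per-protocol analysis cannot fill the gap, because it inherits the same restriction. Protocol Version 3.2 (04 August 2016) is later than SAP 3.0 and still carries the unrestricted mITT, so the two documents disagree on who is in the primary analysis. What is at stake is whether a DCR estimate depends on the restriction, in a design with about 21 patients per Part 1 cohort and 16 per schedule in Part 2.

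**Working it through.** **1. Which planned DCR analyses include a patient without measurable disease?**

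| Analysis | Cohort A | Cohorts B, C |
|---|---|---|
| RECIST 1.1 DCR, mITT | no | no |
| RECIST 1.1 DCR, per-protocol | no | no |
| RECIST 1.1 DCR, mITT Extended | not planned | not planned |
| GCIG DCR, GCIG Evaluable | yes, with baseline CA-125 | not applicable |

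The GCIG analysis also counts CA-125 response and progression (SAP Tables 4-1 to 4-3), so it is a different endpoint from the primary one.

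**2. Timing.** From 29 April 2015 to 07 April 2016 is 344 days. The Version 2.0 entry (SAP 8.1, 20 April 2015) lists a different mITT change. The Version 3.0 entry reports the redefinition of the efficacy populations and the arrival of mITT Extended, but does not name the measurable-disease criterion. The date of that criterion is therefore an inference.

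**3. Reproducing the plan's figures.** Inputs: H0 "true disease control rate ≤ 0.25" against H1 "true disease control rate ≥ 0.50" (Protocol 8.1); "all tests conducted at the one-sided 0.10 level of significance for Part 1" (SAP 3.2); 8 patients in Stage 1 and an implied 3 or more to continue (SAP 3.12); about 21 evaluable per cohort (Protocol 3.2). The power statement is redacted, so 80% is assumed. For a total of n patients and success at 8 or more,

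P(success) = Σ over x = 3 to 8 of b(x; 8, p) × P(Y ≥ 8 − x), with Y ~ Bin(n − 8, p).

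The optimal design under 80% power is 8 then 21, continuing at 3 and succeeding at 8, with exact alpha 0.098 and power 0.811. This matches the stated 8, 3 and 21. At 85% and 90% power the optimal designs are 11/24 and 10/27, which do not match. The exact Stage 1 intervals in Protocol 1.3 also reproduce: 6/8 34.9–96.8; 5/8 24.5–91.5; 2/8 3.2–65.1.

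**4. Effect on the estimate (illustration).** The exact lower one-sided 90% bound for x of n is the 0.10 quantile of Beta(x, n − x + 1).

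| Assumed exclusions | All treated | Measurable only |
|---|---|---|
| 2, none controlled | 8/21 = 38%, bound 23.6% | 8/19 = 42%, bound 26.3% |
| 3, none controlled | 8/21 = 38%, bound 23.6% | 8/18 = 44%, bound 27.9% |
| 3, all controlled | 11/21 = 52%, bound 36.4% | 8/18 = 44%, bound 27.9% |

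In the first two rows the bound moves across 25%, but the reconstructed Simon decision does not change: 8 successes meet the rule before and after. In the third row the restriction lowers the DCR.

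**5. Effect on error rates (conditional).** If k of 21 are lost, all from Stage 2, and the cut-off stays at 8:

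| k | n | alpha | power at 50% |
|---|---|---|---|
| 0 | 21 | 0.098 | 0.811 |
| 1 | 20 | 0.081 | 0.789 |
| 2 | 19 | 0.065 | 0.757 |
| 3 | 18 | 0.050 | 0.713 |

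If 21 patients with measurable disease are analysed, alpha and power are unchanged.

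**The case against.** The case for leaving the SAP alone has several parts.

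- **The change is disclosed** in the section meant for it. Protocol 8.1 leaves analysis details to a SAP finalised before database lock, and Protocol 1.4 (Version 3.2, August 2016) still treats that lock as future. This stands, and it answers any suggestion of concealment. It does not supply the missing comparison.
- **Some of these patients are covered.** A reader might infer that no DCR analysis of any kind includes them. That is wrong for Cohort A, and so for all of Part 2, because of the GCIG analysis. The gap that remains is the RECIST 1.1 endpoint everywhere, and any DCR at all in Cohorts B and C.
- **The number removed can largely be recovered.** SAP 4.1 tabulates the size of each population by cohort and schedule, so mITT Extended minus mITT gives the count. This stands, except that the split by Simon stage is not planned, and a count does not show the effect on DCR.
- **Sample size.** A reader might infer that the analysed number falls below 21, or below 16 per schedule. The documents do not show this. Part 1 targets evaluable patients, SAP 3.13 ties the final analysis to reaching the target number evaluable for DCR, and the text that might define evaluable is redacted.
- **Motive.** A reader might infer that the results drove the change. Nothing supports that. The read-out covered only 8 patients per cohort and was itself in evaluable patients, with the definition then in force unknown.
- **Redaction.** Part of SAP 5, the table list and the shells are blacked out, so an extended-population DCR table cannot be ruled out. The wording of SAP 2.1 makes it unlikely.

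**Conclusion.** The point holds in limited form and should be fixed. The SAP's primary population is narrower than the protocol's and leaves out patients whom the protocol admits. In the visible text, the RECIST 1.1 DCR is never shown with those patients included. For Cohorts B and C no DCR analysis of any kind includes them.

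The size is unknown, because neither document gives the number of evaluable-only patients or their outcomes. With three of 21 assumed excluded, the DCR could rise by about 6 percentage points (38% to 44%) or fall by about 8 (52% to 44%). The first case moves the reported lower bound from below to above the 25% null but leaves the reconstructed Simon decision as it was. Power would fall from 0.81 to 0.71 only if the 21 evaluable patients include three without measurable disease, all three are lost from Stage 2, and the cut-off stays at 8. The same loss would take alpha from 0.098 to 0.050. These error rates rest on the assumed 80% design power. That the restriction came after the Stage 1 read-out is likely from the revision history but is not stated.

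**What to change.** In SAP 2.1, extend the stated use of mITT Extended to DCR. In SAP 4.3.1, name a RECIST 1.1 DCR sensitivity analysis on that population for each Part 1 cohort and for the Part 2 comparison, with the same intervals and Fisher's exact test as the primary analysis. State the classification rule: patients without measurable disease who are non-CR/non-PD and free of progression to at least 77 days count as disease control. Next to each DCR, show how many patients the measurable-disease criterion removes, by cohort, Simon stage and schedule.

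The cost is one more table. No new data are needed, because these patients are already scanned on the study schedule and the population is already defined.
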